2. OBJECTIVES

Primary Objective

With this study, in patients with an unknown metabolic phenotype, we want to identify the genetic cause and align it with its biochemical and phenotypical abnormalities. Moreover, with joined forces of the UMD we would like to pave way for implementation of these extended genetic and omics techniques in clinical care. Only with a solid genetic diagnosis patients will be able to receive (future) treatment, prognostication and patient's families can receive proper counselling, including reproductive options.

Secondary Objective(s):

- 1) identification and validation of novel, IEM related, genes/phenotypes/pathways
- 2) to study how omics and genomics complement each other in diagnosing rare disease (genetic cause, biomarker, pathophysiology, natural disease history)

3. STUDY DESIGN

This is a national multicenter prospective diagnostic study. The study is expected to run for at least 5 years.

4. STUDY POPULATION

4.1 Population

A total of 500 (in)capacitated patients (any age/gender) will be included, with an unexplained metabolic phenotype (see inclusion criteria), in whom no conclusive diagnosis has been established after extensive 'standard of care' clinical work-up (see inclusion criteria). Patients will be referred from the outpatient clinics of all participating university medical centres in the Netherlands: paediatrics, internal medicine, neurology, clinical genetics and psychiatry.

4.2 Inclusion criteria

Patients with an unexplained metabolic phenotype defined as: neurological symptoms and/or abnormalities on (physical) examination suggestive of an inborn error of metabolism (energy deficiency, intoxication type or storage type):

Energy deficiency: neurological (repeated rhabdomyolysis, verified exercise intolerance, neuropathy, myopathy, ataxia), ophthalmological (retinitis pigmentosa (RP)), otological (hearing loss, deafness), endocrine (hypoparathyroidism, hypoglycemia)

Intoxication: neurological (encephalopathy, regression, movement disorder, psychiatric symptoms), ophthalmological (lens luxation), organic (liver and kidney function abnormalities)

Storage: neurological (regression, psychiatric symptoms), ophthalmological (cataract/corneal clouding), skin (angiokeratomas), blood (cytopenias), organic (hepatosplenomegaly, cardiac hypertrophy, skeletal abnormalities, short stature, coarse facial features, umbilical/inguinal hernia)

AND / OR

one or more of the following suggesting a deficient metabolic pathway or process:

- abnormal metabolites in body fluids (CSF, urine, blood)
- functional studies at a biochemical/cellular level indicative of a metabolic deficiency (e.g. respiratory chain complex analysis)
- organ dysfunction (e.g. liver or kidney failure)
- an abnormal clinical function test (protein loading test, fasting test, meal test, validated exercise test, non-ischaemic underarm test)
- abnormalities on imaging (neuro-imaging (including spectroscopy); X-rays (dysostoses or other bone abnormalities); ultrasound (enlarged liver/spleen))
- a VUS (variant of unknown significance) in a gene involved in metabolism

AND

no diagnosis despite extensive clinical, metabolic and genetic investigations

- SNP-array/array-CGH: inconclusive results
- metabolic screening according to up to date clinical protocols: inconclusive results
- WES (open or gene panel): no class 4 or 5 variants in a known (OMIM annotated) disease related gene that can fully explain the phenotype of the patient

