In general, symptoms of patients with an IEM are heterogeneous, affecting one or multiple organ systems and are often progressive in nature. Patients can have neurological (repeated rhabdomyolysis, exercise intolerance, neuropathy, myopathy, ataxia), ophthalmological (retinitis pigmentosa (RP)), otological (hearing loss and/or deafness) and/or endocrine abnormalities (hypoparathyroidism, hypoglycemia) as consequence of energy deficiency. In other IEMs endogenous intoxication causes neurological signs (encephalopathy, regression, movement disorder, psychiatric symptoms), ophthalmological (lens luxation) or organic abnormalities (liver and kidney function abnormalities. Storage associated IEMs, caused by enzyme deficiencies, can lead to yet different neurological (regression, psychiatric symptoms), ophthalmological (cataract/corneal clouding) and organ abnormalities (hepatosplenomegaly, cardiac hypertrophy, skeletal abnormalities, short stature, coarse facial features, umbilical/inguinal hernia). Many of the above mentioned features are disabling. Patients and family members hope to find therapies. They are often worried about the risk of recurrence of the disorder and future prospects. Without an accurate genetic diagnosis, these worries and questions cannot be addressed.

In current daily practice, patients with an unexplained metabolic phenotype, as outlined above, are seen by different medical specialists (e.g. ophthalmologists, endocrinologists, psychiatrists, neurologists, paediatricians, clinical geneticists). There is no standardized diagnostic evaluation of these patients; the presentation at the first specialist often determines the order in which diagnostic tests take place, which can vary from an eye examination, a cerebral MRI scan, cytogenetics to an exome or metabolomic testing.

Commonly, there are 2 main diagnostic trajectories that can be applied:

- 1) *targeted metabolic screening in plasma, urine and/or cerebral spinal fluid (CSF).*

When an abnormal metabolite pattern is identified, fitting with a known IEM, targeted DNA diagnostics are performed, to confirm the clinical diagnosis.

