- 2) *targeted genetic testing through Sanger sequencing (in case of a strong clinical suspicion), gene panels consisting of several genes associated with a certain phenotype (e.g. movement disorder), targeted exome sequencing (exome-based panels) or true open trio-WES analysis (often analysis of the clinome which comprises all genes published associated with a human disease, correlating the variants found in the affected person to his/her parents to identify Mendelian disorders).*

There are several potential outcomes of this trajectory:

- 1) A known pathogenic IEM profile or mutation in a gene previously reported to cause a an IEM, fitting with the patient's features leading to a diagnosis.
- 2) In the remaining 50% (or more) no etiologic diagnosis is established, with two possible scenarios:
 - A DNA variant of unknown significance (VUS) in the WES and/or a metabolic alteration in metabolic investigations is/are identified, which cannot be unified into a confirmed diagnosis.
 - No clues arise from (both) the above mentioned diagnostic trajectories

Causes for inconclusive results in undiagnosed patients with metabolic phenotypes

The reasons why a patient remains undiagnosed is that certain phenomena are not being picked up by the current standard test used in clinical care. Using WES it is known that certain types of genetic alterations (e.g. repeat expansions, mutations in the mitochondrial DNA, intronic mutations) are not identified. In addition, some parts of some genes have low coverage (for instance due to CG-enriched genes or mosaicism) (Pena et al., 2018; Zeiger et al., 2018). Metabolic analysis is based on a broad set of screening tests. In these tests not all metabolites are detected. Untargeted Metabolomics is relatively new and has not been implemented in clinical care settings.

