We aim to include 500 undiagnosed patients suspected of having and IEM from all six clinical centers. The study will last at least 5 years; we expect to enrol on average 100 patients per year. The overall aim of this study is to diagnose patients with an unknown metabolic phenotype. In addition, we want to provide evidence that the combination of approaches and techniques used in this study will increase diagnostic yield compared to current separated approaches. With increasing diagnosis in patients with IEM, more knowledge on natural disease history and pathophysiological background will be gained, paving way for future therapeutics. In addition, families can receive proper counselling and will have options for reproductive choices.

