8.3 Study procedures

See Figure 1, pag24

pigmentosa (RP)), endocrine (hypoparathyroidism, hypoglycemia)

Intoxication: neurological (encephalopathy, regression, movement disorder, psychiatric symptoms), ophthalmological (lens luxation), organic (liver and kidney function abnormalities)

Storage: neurological (regression, psychiatric symptoms), ophthalmological (cataract/corneal clouding), organic (hepatosplenomegaly, cardiac hypertrophy, skeletal abnormalities, short stature, coarse facial features, umbilical/inguinal hernia)

² abnormal: metabolites in body fluids (CSF, urine, blood)/ Functional studies at a biochemical/ cellular level/radiological (neuro)imaging suggesting a deficient metabolic pathway or process and/or a VUS (variant of unknown significance) in a gene involved in metabolism

* adult/pediatric metabolic physician, neurologist, psychiatrist, clinical geneticist

Patient referral

Patients with an unexplained metabolic phenotype are eligible for inclusion in the study (see inclusion criteria 4.2, pages 19-20) *only* once all ‘standard of care’ clinical diagnostic tests have proved inconclusive (see inclusion criteria 4.2, pages 19-20). Thus, no clinical diagnostic procedures will be postponed because of participating in the study.

The treating physician will ask the patient for consent to share his/her data with the multidisciplinary clinical meeting of the ZOEMBA team. After patient consent, the referring specialist will make a patient resume, using a standard format, which will be used for discussion at the multidisciplinary patient meeting the “ZOEMBA-team triage meeting” (1x per 2-4 weeks).

The ZOEMBA team for this meeting exists of:

- Study coordinators: Dr. [name] (Study PI, Pediatrician in Inborn errors of metabolism & Biochemical Geneticist– Amsterdam UMC), Dr [name] (internal medicine specialized in IEM), Prof [name] (Study CoPI, head of the Laboratory of Metabolic Diagnostics, UMC Utrecht), Dr. [name] (coordinating postdoctoral fellow, clinical geneticist specialized in IEM, Amsterdam UMC)
- A clinical and laboratory representative per participating UMC (when not already represented by the study coordinators):
 - Amsterdam UMC: Prof. dr. [name] (PI at the laboratory of GMD), Dr [name] (Clinical Chemist IEM, Laboratory GMD, specialized in lipidomics)

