10. STATISTICAL ANALYSIS

The only statistics will be a descriptive analysis on the number of patients included. We will also report the number of patients with a confirmed diagnosis and the average time to diagnosis.

10.1

Not applicable

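### Patients may enter after a panel-only exome reading, and the pooled count of diagnoses cannot separate the gain from WGS and omics from what a first open reading of the exome would have found

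*Protocol*

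**What the plan says.** - **Entry (section 4.2).** The earlier sequencing must meet this condition: "WES (open or gene panel): no class 4 or 5 variants in a known (OMIM annotated) disease related gene". The words "WES (open or gene panel" let an open and a panel-restricted reading qualify equally. Because the criterion names WES, I take the panel to be a filter on exome data, most of which has then not been looked at.
- **Current practice (section 1, on current diagnostic trajectories).** The genetic route includes "targeted exome sequencing (exome-based panels) or true open trio-WES analysis", alongside Sanger sequencing and gene panels. It is introduced with "Commonly, there are 2 main diagnostic trajectories that can be applied", and the same part says that the work-up is not standardised.
- **Standard care first (section 8.3).** Patients are eligible only once all standard-of-care "clinical diagnostic tests have proved inconclusive", with a reference back to section 4.2.
- **Step I (summary, section 8.3 and Amendment 2).** Every participant gets a reanalysis of the earlier exome, metabolomics and WGS. A known genetic diagnosis at this step ends participation.
- **Endpoint (section 8.1.1).** A causal (likely) pathogenic variant counts, whichever test found it.
- **Aim (section 1, on this study).** The investigators want evidence that the combined approach "will increase diagnostic yield compared to current separated approaches". Section 2 adds the question of how omics and genomics complement each other.
- **Analysis (section 10).** "The only statistics will be a descriptive analysis on the number of patients included", to which the section adds the number of confirmed diagnoses and the average time to diagnosis. Sections 10.2, 10.3 and 10.5 are marked not applicable.

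**The concern.** For someone whose exome was opened before referral, the Step I reanalysis is a second look. For someone who had a panel only, it may be the first open look, and so a test that some patients already receive outside the study. Both kinds of diagnosis enter the same total.

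This matters because of the comparison that the protocol wants to make. A diagnosis that a currently used test could have produced is not a gain over current practice. If the pooled yield is read as that gain, the error runs in one direction, upward. It grows with the number of panel-only patients, so it depends on referral mix. Section 4.4 already expects referral and enrolment numbers to differ between centres. The result is meant to support use of these techniques in clinical care, so readers will want to know what WGS and omics add beyond an opened exome.

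**Working it through.** **1. The plan's own figure.** Section 4.4 gives a yield of 33%, compares it with 34% in a cited programme, and expects 170 diagnoses, 20 of them with novel candidate genes.

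- 500 × 0.33 = 165, and 500 × 0.34 = 170.
- 500 / 25 = 20 novel candidates.

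The stated 170 is reproduced exactly at 34% and within 3% at 33%. I use 165 below. There is no hypothesis test or power statement to check.

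**2. Diagnoses supplied by a first open reading.** Let *f* be the share of participants who enter after a panel-only reading, and *y* the yield of opening the exome in those patients. Then:

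- diagnoses D = 500 × f × y
- yield points = 100 × f × y
- share of expected diagnoses = D / 165

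The protocol gives neither *f* nor *y*, so both are assumptions. Two figures in section 1 give some orientation for *y*. The first is 10%, from reanalysis of 40 clinical exomes, which were not panel-only exomes. The second is 25–30%, the yield of WES in large general series. The second is best taken as an upper bound. If a panel alone solves a fraction P of patients and open WES solves Y, the yield left among panel-negative patients is (Y − P)/(1 − P), which cannot exceed Y. The 5% column is an assumed low value.

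Each cell gives diagnoses, then yield points, then share of 165:

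| f | y = 5% | y = 10% | y = 25% | y = 30% |
|---|---|---|---|---|
| 10% | 2.5; 0.5; 1.5% | 5; 1.0; 3.0% | 12.5; 2.5; 7.6% | 15; 3.0; 9.1% |
| 25% | 6.25; 1.25; 3.8% | 12.5; 2.5; 7.6% | 31.25; 6.25; 18.9% | 37.5; 7.5; 22.7% |
| 50% | 12.5; 2.5; 7.6% | 25; 5.0; 15.2% | 62.5; 12.5; 37.9% | 75; 15.0; 45.5% |

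**3. What remains beyond the opened exome.** Suppose the 33% includes these diagnoses. At y = 10% the remainder is 33 − 2.5 = 30.5% for f = 25%, and 33 − 5.0 = 28.0% for f = 50%.

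**4. Comparison with sampling error.** The 95% half-width at 33% and n = 500 is 1.96 × √(0.33 × 0.67 / 500) = 1.96 × 0.0210 = 4.1 points. A shift of 2.5 to 5 points is of the same order, and a larger sample would not reduce it.

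**5. Whether the planned reporting could recover the split.** Section 10 gives one count. Section 8.1.3 names the yield of the approach as a whole and the yield of integrated analysis for validating causality. Neither divides diagnoses by type of earlier exome reading or by the test that found the variant. Since Amendment 2, WGS runs in Step I for everyone and also covers the coding regions. The same variant can therefore appear in both data sets, and the protocol has no rule for which test gets the credit.

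**The case against.** The strongest reply is that exome reanalysis is part of the package. Section 1 lists it first among the new diagnostic possibilities, the summary gives it to all participants, and section 8.1.3 defines yield as that of the approach used. A diagnosis made by reading the exome is then legitimate study yield. This stands. A reader might infer that the overall yield is inflated, and the documents do not support that. Only its reading as a gain over current practice, or as the contribution of WGS and omics, is affected.

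A reader might also infer that panel-only entry breaks the protocol's rule that standard care be exhausted. That does not follow either. Open trio-WES is one alternative in a work-up that the protocol calls unstandardised, and section 8.3 refers to section 4.2 for what is required. A panel-only patient can have completed standard care as defined here.

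It is also fair to say that there is no comparator arm, that no numerical gain is planned, and that the comparison appears in the Introduction and not in the endpoints. That limits the weight of the point but does not remove it, because the aim is stated and the pooled count is the only yield figure in section 10.

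The exclusion in section 4.3 for suspected conditions with an easier and cheaper test may remove some of these patients. It does not require the exome to be opened before entry.

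Finally, a yield table could be left to a statistical analysis plan. Section 10, however, is worded as a complete list of the statistics, and the information about the earlier exome has to be collected at entry.

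**Conclusion.** The point holds in a limited form. Section 4.2 mixes patients with opened and panel-restricted exomes, and section 10 pools their diagnoses. The count is valid for the package but cannot carry the stated claim of a gain over current approaches, and reading it that way is biased upward.

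The direction is clear from the text, but the size is not. With an assumed panel-only share of 25–50% and an assumed yield of 10%, a first open reading would supply about 12.5–25 of 165 diagnoses, or 2.5–5 yield points. The columns at 25–30% mark a ceiling and should not be quoted as an expectation, because those yields come from patients not selected for a negative panel. This is a gap in attribution that should be closed. It does not undermine the primary endpoint.

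**What to change.** 1. Record two items at entry: whether the earlier exome was read openly or through a panel only, and the date of its last analysis. The date also separates a recent open reading from an old one.
2. In section 10, report yield by type of earlier reading and by the test that made the diagnosis.
3. State an attribution rule before results are known. For example, a variant visible in the existing exome data is credited to exome reading even if WGS also finds it, and the gain from WGS and omics is counted only beyond that. Section 12.1 already places the earlier exome data in the research environment, so the rule can be applied.

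The cost is two entry fields, one more table and a short rule. The protocol does not say whether the referral summary already holds these fields, but the earlier exome result has to be seen to apply section 4.2. No patient is lost and no procedure is added. The drawback for the investigators is that the gain they can claim for WGS and omics may turn out smaller.

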4.3 Exclusion criteria

A patient will be excluded from participation in this study if:

- after discussion by the ZOEMBA team (see Methods) he/she is suspected to have:
 - a genetic condition for which there is a simpler and more cost-effective test available for diagnosis
 - a complex genetic disorder (caused by a combination of multiple genes and/or environmental influences)
 - a condition that is thought to be caused by factors that are non-genetic, such as infection, injury or toxic exposure
- he/she is unable to follow the study protocol (e.g. additional blood samples)

4.4 Sample size calculation

A previous study in 47 (predominantly pediatric) patients with unexplained ID plus metabolic phenotypes (executed by the principal and coordinating investigator of the current study) showed a high diagnostic and discovery yield using an integrated approach with deep phenotyping, WES and metabolomics followed by functional analyses; a diagnosis was established in 68% of all patients plus a novel human disease gene identified in 11 patients. 44% of these diagnoses were amenable to causal therapies, including specific dietary restriction, supplementation or pharmacologic interventions.

In the proposed study, which focuses on unsolved cases after standard diagnostic trajectories and with inclusion of adults with more diverse phenotypes, we expect the yield to be lower. We make a conservative estimate of a diagnostic yield of 33% (comparable to findings from the NIH Undiagnosed Diseases Program of 34% (Gahl et al., 2016; Splinter et al., 2018)), and an expected discovery rate of a novel candidate gene 1 in 25.

Thus, we estimate to diagnose 170 patients, including 20 with novel candidate disease genes. With an inclusion period of at least 5 years, we expect to enrol on average 100 patients per year. The number of patients referred and / or enrolled per year will likely differ per UMC based on expertise and focus. A recent investigative query among the 6 UMCs has shown that our aim of enrolling 500 undiagnosed patients suspected to have an IEM is realistic based on their annual patient numbers and diagnostic trajectories.

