Methods used: Patients with unexplained metabolic phenotypes are referred (on paper) and discussed by the ZOEMBA (Zoektocht naar Erfelijke MetaBole Aandoening) team. Clinical phenotyping, bioinformatic reanalysis of WES data and additional metabolomics will be performed in all participants. In case still no diagnosis is made, a tailormade diagnostic plan is made combining deep WES, WGS, glycomics, lipidomics, epigenomics, transcriptomics and/or proteomics leading to: a known IEM, a candidate variant or no diagnosis. In case of a

variant, additional functional studies (enzymatic assays, targeted omics, CRISPR/CAS, cell lines) will be performed to confirm the effect of the genetic variant on protein function. When still no diagnosis is established, matchmaking (genetic/phenotypical) through international databases might lead to a diagnosis.

Nature and extent of the burden and risks associated with participation, benefit and group relatedness:

The study involves collection of clinical data, reanalysis of previously analysed genetic data, additional “omics” and functional testing. All participants will have between 1 and 3 clinical visits for this study (at the UMC of referral) and a maximum of 2 telephone appointments with the arts-onderzoeker. Whenever possible study visits will be combined with regular hospital visits. Clinical data (clinical history, family history, physical examination, consultations, additional laboratory and/or radiological investigations) will be collected. A physical examination and blood and urine sampling will be performed in all participants at their first study visit. Any other already available biological samples (eg stored cell lines, dried blood spots, cerebrospinal fluid (CSF)) will be collected for re-analysis. For a selection of patients a skin biopsy will be performed at the 2nd clinical study visit for the use of functional studies. Potential burdens for participants are: the additional study visit(s), diagnostic procedures (e.g. blood, urine sampling and skin biopsy), as well as renewed (false) hope/uncertainty about finding a diagnosis. The potential benefit for all participants include: the opportunity to establish a diagnosis providing information on prognosis, (refinement of) management, genetic counselling with precise recurrence risk and option(s) for prenatal diagnosis.

1. Introduction and Rationale

Background: Rare Diseases (RD) and Inborn Errors of Metabolism (IEM)

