8. METHODS

8.1 Study parameters/endpoints

8.1.1 Main study parameter/endpoint

The primary endpoint of this study is the identification of genetic variant(s) in an affected patient and establishment that this/these genetic alteration(s) is/are (likely) pathogenic (with a deleterious impact on protein function; ACMG class IV or V) and causal of disease.

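### Does the estimate of 170 diagnoses in section 4.4 overstate what the primary endpoint can be expected to deliver?

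*Protocol*

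**What the plan says.** Protocol section 4.1 fixes the size of the cohort: "A total of 500 (in)capacitated patients (any age/gender) will be included". Section 4.4 gives the planning yield, "We make a conservative estimate of a diagnostic yield of 33"%, and calls it "comparable to findings from the NIH Undiagnosed Diseases Program of 34"%. It adds "an expected discovery rate of a novel candidate gene 1 in 25" and concludes: "Thus, we estimate to diagnose 170 patients, including 20 with novel candidate disease genes".

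Under section 8.1.1 the primary endpoint is met when variants are identified in a patient and it is established that the alteration "is/are (likely) pathogenic (with a deleterious impact on protein function; ACMG class IV or V) and causal of disease". The Summary (Methods used) describes the tailored work-up as "leading to: a known IEM, a candidate variant or no diagnosis". Section 8.3 sends a candidate variant to Step IIA, where additional tests examine causality. If the results fit the phenotype and a diagnosis can be made, the patient moves to the outcome for a known genetic diagnosis. If not, causality stays open and matching through the international database continues.

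Section 10 limits the statistics to description: numbers included, numbers with a confirmed diagnosis, and average time to diagnosis.

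**The concern.** Two things look wrong.

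- **The product.** The stated inputs, 33% and 500, do not give the stated output. The result matches the benchmark programme's 34% instead, although the Protocol presents its own 33% as the cautious figure.
- **The numerator.** Section 4.4 places 20 patients with novel candidate genes among those diagnosed. The Summary and section 8.3 keep candidates apart from diagnoses, and section 8.1.1 asks for established pathogenicity and causality. The planning count and the endpoint count might then be different quantities.

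If so, the study could appear to fall short of its own expectation when measured by its primary endpoint. Alternatively, unconfirmed candidates could be counted as diagnoses after the results are known, which would move the reported yield by up to 20/500 = 4 percentage points.

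**Working it through.** **Inputs.** N = 500 (sections 4.1 and 4.4); assumed yield 33%, benchmark yield 34%, novel candidate gene rate 1 in 25, stated result 170 including 20 (all section 4.4).

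**Step 1: reproduce the stated figures.** Expected count = N × rate.

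| Rate | Count | Against the stated figure |
|---|---|---|
| 33% | 500 × 0.33 = 165 | 5 below 170 |
| one third | 500 / 3 = 166.7 | 170 to the nearest ten |
| 34% | 500 × 0.34 = 170 | exact |
| 1 in 25 | 500 / 25 = 20 | exact |

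The literal gap is 170 − 165 = 5 patients, which is 5/500 = 1.0 percentage point, or 5/170 = 2.9% of the stated figure. For scale, the binomial standard deviation of a count with expectation 165 is √(500 × 0.33 × 0.67) = √110.55 ≈ 10.5 patients, so the gap is about half a standard deviation. The Wilson 95% interval around 165/500 is 29.0% to 37.2%, which contains 34%. The observed result could not distinguish the two planning values.

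**Step 2: how much of the 170 meets section 8.1.1?** Let v be the share of the 20 novel-gene patients whose variant is validated to the standard of section 8.1.1.

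- On the 33% basis: 165 − 20 + 20v = 145 + 20v, so 145 (29.0%) at v = 0 and 165 (33.0%) at v = 1.
- On the 34% basis: 170 − 20 + 20v = 150 + 20v, so 150 (30.0%) at v = 0 and 170 (34.0%) at v = 1.

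The Protocol gives no value for v. A shortfall of 20 to 25 patients against 170 (170 − 150 and 170 − 145) requires v = 0, that is, no novel-gene case ever confirmed. At v = 1 the shortfall is 0 to 5.

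**Step 3: does the text force v = 0?** It does not.

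- Section 8.1.1 sets a standard of evidence for the variant and says nothing about whether the gene was known before.
- In section 8.3 a candidate variant is a stage in the work-up, with an explicit route to a diagnosis after Step IIA.
- The first secondary objective in section 2 couples finding novel genes with validating them.
- Section 4.4 can be read as 20 diagnosed patients whose disease gene is novel, with the word candidate describing the standing of the gene rather than an unresolved case.

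**Step 4: what depends on 170?**

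- Section 4.4 supports the 500 by a query among the six centres, not by a precision or power calculation.
- The evaluation after one year (section 9.5) looks at inclusion.
- Premature termination (section 8.7) is tied only to no patients being included.
- Section 10 states no hypothesis or threshold.

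No decision in the Protocol takes 170 as an input.

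**The case for a change.** The strongest case for acting is that one multiplication introduced as a consequence should match its inputs, and that 170 is the only numerical expectation the Protocol gives for its primary outcome. Section 4.4 also describes the earlier 47-patient study as having diagnoses plus novel genes, but includes the novel genes within the diagnoses for this study without saying why. With the status of the 20 unstated, the headline yield could in principle be settled after the fact.

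Part of this stands. The yield and the count do not agree to the digit, and section 4.4 does not say whether the 20 are expected to be validated. The rest does not carry. What may be counted is fixed by section 8.1.1 and by the confirmed-diagnosis wording of section 10, not by the planning estimate. A rule that candidates count only once causality is established would largely repeat what sections 8.1.1 and 8.3 already say.

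Rewriting section 4.4 to expect 145 patients (29%, exact 95% interval 25.1% to 33.2%) would be worse than leaving it. That count assumes zero validation, which has no source in the Protocol, and the interval would lend it false precision.

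**Conclusion.** The concern does not call for a change. The arithmetic point is a loose rounding or a mix of 33% and 34%, worth 5 patients or 1 percentage point. The endpoint point is an ambiguity of wording: depending on an unstated validated share, the expected primary count is 145 to 165 on the 33% basis or 150 to 170 on the 34% basis. An overstatement against 170 of anywhere from 0 to 25 patients is compatible with the text, and none is demonstrated.

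This conclusion rests on two readings. The first is that 170 is an expected yield and not a success criterion, which the absence of any threshold in section 10 supports. The second is that analysts will count a patient as diagnosed only when section 8.1.1 is met, which is what the Protocol directs. On that footing the cohort size, the endpoint, the analysis and the reported result are the same whether section 4.4 says 165 or 170. Stating one yield with its matching count, and the status of the 20, would be good editing if the section were reopened for another reason.
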